7.3 Non-serious adverse events

Non-serious adverse events (NSAEs) do **not** fulfil the formal criteria specified in 7.2. **All non-serious adverse events** must be documented in the system and sent **within 10 days** of becoming known. Exception: In the event that entering an NSAE in the eCRF is not possible for technical or other reasons, a paper form for documenting and reporting the AE directly to **adverse** can be requested and then forwarded to the following fax number.

If sent by fax, the date of the fax is to be written on the original report form, which remains in the study documentation at the study site.

If the information on the non-serious adverse event is provisional in nature, it should be finally completed as soon as possible and sent to Novartis as an NSAE follow-up.

7.4 Details of the causality assessment

For assessing the causal relationship between Afinitor[®], exemestane and/or other concomitant medication and the event that has occurred, the options **"no causal relationship" or "causal relationship suspected"** are available. A physician's causality assessment is required and must be documented in all cases.

Relationship with Afinitor®, exemestane and/or other concomitant medication

It should be noted that many different aspects can play a role in assessing causality. These aspects can include the individual patient, the underlying disease, any concomitant medication or non-pharmacological factors.

No causal relationship	There is no reasonable possibility of a causal relationship
	between Afinitor [®] , exemestane and/or other concomitant
	medication with the AE.
Causal relationship suspected	There is a reasonable possibility of a causal relationship
	between Afinitor [®] , exemestane and/or other concomitant
	medication with the AE.

7.5 Handling side effects of other drugs from Novartis

Adverse events that are suspected to be in causal connection with Novatis drugs other than the drugs studied in this NIS will have to be announced in the range of the legal notification to the Arzneimittelkommission der deutschen Ärzteschaft (AkdÄ) and Novartis DS&E (Novartis Pharma GmbH, Abteilung Arzneimittelsicherheit, [name] Fax:

) as a spontaneous message (individual case message outlying the study). This includes suspicions of side effects under therapy with a Novartis drug which are known already before or during the screening visit and which have not yet been reported.

7.6 Side effects of drugs from other manufacturers

Suspected cases of side effects in connection with drugs from other manufacturers that are not included in the defined aims or reason for conducting the non-interventional study must be reported by the participating physician to the supreme federal authority (BfArM or PEI), the Drugs Committee of the German Medical Association (AkdÄ) or to the marketing authorisation holder of the respective product (exception: suspected interaction with a Novartis product, see 7.6). The study drugs in this NIS are Afinitor[®] and exemestane.

7.7 Progression of the underlying disease (tumour progression)

Deterioration of the underlying disease (tumour progression) during treatment with Afinitor[®] must be documented as an adverse event (AE) only if a causal relationship with Afinitor[®] treatment is suspected or if as a result of disease progression one or more of the formal criteria for a serious adverse event (SAE) listed under point 7.2 applies.

7.8 Abnormal laboratory values or test results

Abnormal laboratory values or test results should be documented as an adverse event only if they

- are above or below normal/reference values AND
- represent a change in terms of deterioration of the respective parameter compared with the baseline finding. This condition does not apply if there is no previous baseline value, **AND**
- the changed laboratory parameters
 - o are considered clinically relevant OR
 - \circ are associated with clinical symptoms **OR**
 - require therapeutic intervention **OR**
 - lead to a dose reduction and/or temporary suspension or permanent discontinuation of Afinitor[®] and/or exemestane.

Changes in a quantifiable parameter are to be documented as a **serious adverse event** if the formal criteria for an SAE are fulfilled (see 7.2). Reporting deadlines and reporting procedures are the same as those specified under 7.2 (Serious adverse events) and 7.4 (Non-serious adverse events).

7.9 Documentation of exposure during pregnancy and use during lactation

The authorisation for the combination of Afinitor[®] with exemestane is for postmenopausal patients. If it is nevertheless taken by a mother during pregnancy and/or lactation, all pregnancies that existed or occurred during this NIS, regardless of whether they are associated with an AE/SAE or not, must be reported to the address given above within 24 hours of becoming known using the

report form for pregnancies. Any use during lactation must also be documented and reported in the same way.

7.10 Patient questionnaires (e.g. quality of life questionnaires)

The events that enquired about in the validated and standardized patient questionnaire EORTC QLQ-C30/BR23 and the questionnaires on physical activity need not be documented additionally in the eCRF as adverse events. These entries describe the respective clinical picture and its course and are therefore analysed and presented separately. However, the physician involved must review all completed questionnaires (EORTC QLQ-C30/BR23, questionnaires on physical activity, questionnaire on stomatitis prophylaxis), also taking into account the answers relating to the presence of adverse events (AEs) in the patient questionnaire filled out at the previous assessment time, reporting these by documenting them in the eCRF. Any additions made that go beyond the respective questionnaire layout must be checked by the participating physician for the presence of an AE or SAE and documented in the eCRF if necessary.

8 Ethics

8.1 Consultation with the ethics committee

In accordance with the joint recommendations of BfArM and PEI on the planning, implementation and evaluation of observational studies and the VFA recommendations for improving the quality and transparency of non-interventional studies, an ethics committee with responsibility for the medical director, constituted according to federal state law, will be consulted before the start of the study. In this case, this is the ethics committee of **Constituted according**.

8.2 Patient information and informed consent form

Every patient must be given information by the treating physician about the aims and the nature and scope of documentation before being included in the NIS. Because an authorised drug is being observed in the NIS, specific patient information that goes beyond the scope of the instructions for patients is not needed.

A patient may not be included in the NIS without her written consent to having her data documented in the NIS and to having her patient file viewed for comparing data. Processing of personal data for the purpose of comparing the data collected with the patient's medical record (SDV) is subject to EU Directive 95/46/EC and national data protection regulations.

8.3 Data protection

The protection of patient data is assured. Patient data collected in the NIS are documented in pseudonymised form in the observation form, i.e. marked only with a number (patient number) and without indicating the name, initials, date of birth or address of the patient.

If the study results are published, the personal data may be used only in pseudonymised form. The personal data may be viewed only by persons who are authorised by the sponsor and required to maintain confidentiality and by the responsible regulatory authorities where necessary to check that the non-interventional study was properly conducted.

The medical personnel responsible for transferring the data from the patient file must be informed of their data protection responsibilities.

9 Legal and regulatory principles, reporting requirement

This NIS is conducted in accordance with the Novartis Pharma GmbH internal SOPs, which are based on the following recommendations and guidelines:

- Section 4 para. 23 sentence 3 of the German Drug Law (AMG)
- The non-interventional study is notified before its start to the Federal Institute of Drugs and Medical Devices (BfArM), the National Association of Statutory Health Insurance Physicians and the Central Federal Association of Health Insurance Funds pursuant to Section 67, para.
 6 AMG.
- Section 63 b of the German Drug Law (AMG)
- Directive 2001/83/EC of the European Parliament and of the Council and amendment with Directive 2010/84/EU of the European Parliament and of the Council
- Pharmacovigilance Guidelines of Volume 9A of 'The Rules Governing Medicinal Products in the EU'
- Guideline on good pharmacovigilance practices (GVP), Module VI Management and reporting of adverse reactions to medicinal products
- Joint recommendation(s) of the Federal Institute of Drugs and Medical Devices and Paul Ehrlich Institute for the planning, conduct and evaluation of observational studies (7.7.2010)
- The study is also registered before the start in the publicly accessible register for NIS at the VFA (http://www.vfa.de/de/forschung/nisdb/).
- VFA recommendations on improving the quality and transparency of non-interventional studies dated 31/01/2007 and 23/04/2007
- FSA Code of Conduct on collaboration with professionals Federal Gazette dated 07/05/2008

10 Data Management

10.1 Data Management Plan

All quality assurance measures in data management are set out in a project-specific data management plan (DMP) and specified for the individual phases of data management:

- Automatic plausibility checks for data input

- Data query plan, with catalogue of questions that lead to queries at the study site
- Implementation of an audit trail in accordance with FDA CFR21 Part 11 Standard
- Ensuring the integrity of data through documented closure of the data bank
- Data handling report for handling ongoing data inconsistencies relevant for the analysis. The data handling report is an integral part of the statistical analysis plan (SAP).

All data management processes are based on the SOP of CRO

- Comparison of documentation data and source data for the following variables:

- Prerequisites for documentation
- Demographic data
- Examination times including documentation of examinations conducted at these times
- Documentation of SAEs and NSAEs
- Afinitor[®] and exemestane administration
- Treatment response and reasons for discontinuation of treatment
- Treatment/management of stomatitis, if applicable
- Any concomitant diseases

Monitoring will be conducted by a representative, designated by Novartis. The representative will be trained and certified in a monitoring training programme. The results of the SDV will be documented in a monitoring report.

The study site will be paid €150.00 as remuneration for the time spent on the monitoring visit based on the Fees Schedule for Physicians (GOÄ).

12 Statistical analysis plan

A detailed statistical analysis plan (SAP) will be prepared by **Section** before the start of the NIS, in which

- the statistical database on which the analysis is based is specified, including all adjustments, implementations, and calculations of derived parameters
- the specifications of the analysis collective will be presented in detail
- The (inferential) statistical methods will be specified.

12.1 Statistical analysis rationale

All variables measured in this NIS will be analysed and reported using appropriate statistical methods. The NIS will be analysed using epidemiology methods with primary use of descriptive statistical methods. If inferential statistical methods are used to determine confidence intervals, parameter comparisons stating the probabilities of exceeding limits or (multivariate) statistical methods for evaluating covariates, their results are considered to be purely descriptive. In this exploratory context, no alpha adjustments in multiple statistical comparisons are made.

The following intermediate analyses are planned: focus on physical activity and stomatitis management 6 months after inclusion of approx. 500 patients in the documentation, focus on PFS 12 months after the inclusion of approx. 500 patients in the documentation, and focus on stomatitis prophylaxis, incidence and treatment and on PFS 18 months after inclusion of approx. 500 patients in the documentation.

12.2 Descriptive statistical methods

Variables reaching at least interval level will be presented in tabular form including their sample values (number of valid and missing values, minimum, maximum, 5th percentile, first quartile, third quartile, 95th percentile, median, mean, standard deviation).

For variables at the nominal and ordinal level, distribution of the absolute and relative frequencies will be indicated.

For adverse events, incidences will be reported based on the patient population included and incidence density (number of events/sum of person times in years) according to the MedDRA system organ class and preferred term for adverse events (AEs), serious adverse events (SAEs), adverse drug reactions (ADRs) and serious adverse drug reactions (SADRs). Times of events and survival time analyses will be analysed using the Kaplan-Meier methodology. The derivation and rating of these event times is described in the SAP.

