Physical activity: The nature and scope of physical activity before and during treatment with Afinitor[®] and exemestane will be recorded using two questionnaires in hard copy: the "Godin Leisure-Time Exercise Questionnaire" and the "Physical Activity Scales (PAS)¹" developed at the Institute for Cardiovascular Research and Sports Medicine at the Sports University in Cologne.

Stomatitis management: Documentation of the prophylaxis and the management of stomatitis, as well as the start and end dates of this side effect.

Gathering data from clinical practice on the use of drugs

Sequence of treatment: Prior treatment and the treatment following immediately are recorded: type, duration and reason for termination of previous drug treatment(s) and treatment following directly after ending treatment with Afinitor[®].

Drug exposure: Identifying the number of patients in whom treatment needed to be modified, paused or terminated including the type of dose adjustments and the length of and reason for those adjustments.

Safety and tolerability

Documentation of adverse events, serious adverse events, non-serious and serious side

¹ German title: Körperliche Aktivitäts-Skalen (KAS)

effects during routine use.

Scheme of documentation

Time of data entry	At start of documentation	After approx. 2 weeks	Approx. Month 1	Approx. Months 3, 6, 9, 12 etc. at 3- month intervals	At end of treatment with Afinitor [®] and exemestane
Patient characteristics	Х				
Demography and vital parameters	X		X	X	
Medical history and disease characteristics	X				
Previous treatment	Х				
Current tumour history	Х				
Concomitant diseases	Х				
Patient questionnaires on quality of life and physical activity	X		X	X	
Patient questionnaire on stomatitis prevention		Х	Х	Х	
Prescription of Afinitor [®] and exemestane	Х		Х	Х	Х
Prophylactic measures and stomatitis treatment	Х	Х	Х	Х	
Antiresorptive treatment	Х				
Issuance of calendar overview	Х				
AEs/SAEs		Х	Х	Х	Х
Current tumour treatment with Afinitor [®] (dosage, dose reduction, pauses in treatment, reason for dose adjustment)	X	X	X	X	Х
Reason for discontinuing documentation					Х
Reason for discontinuing treatment					Х
Treatment response				Х	Х
Subsequent treatment					Х

Contents of documentation after combination therapy with Afinitor[®] and exemestane

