- Increasing knowledge of routine treatment of breast cancer and of suitable treatment algorithms. For this purpose, prior treatments and the treatment immediately following Afinitor[®] will be documented, in addition to the nature and duration of previous drug treatment(s) and the reason for their discontinuation.
- Number of patients where the treatment needed to be modified, interrupted or discontinued, including type of dosage modifications, duration and cause of the interruptions.

Stomatitis management:

 Prophylaxis and treatment of stomatitis as an adverse event during routine use of Afinitor[®] in combination with exemestane and concomitant treatments, as well as the start and end dates.

Documentation of adverse events (AEs).

6 Study design

This is a non-interventional study pursuant to Section 4 para. 23 sentence 3 AMG, "in the framework of which information from the treatment of persons with drugs is analysed using epidemiological methods; treatment including diagnosis and monitoring shall be provided strictly in accordance with medical practice, not in accordance with a fixed study protocol; if the study drug is subject to authorization or approval pursuant to Section 21a para. 1, treatment shall also be provided in accordance with the instructions for use specified in the authorization or approval" and is conducted in line with the FSA Code of Conduct and according to the joint recommendations of BfArM and PEI on the planning, conduct and analysis of observational studies as well as the VRA recommendations on improving the quality and transparency of non-interventional studies.

The design of an NIS allows observation without the need to specify strict inclusion and exclusion criteria or interventions. It is therefore suitable for the study aims described, in particular because no requirements regarding the nature and level of physical activity are specified, likewise in relation to prophylaxis and management of stomatitis. Instead, the intention is to describe in a relatively large number of patients the routine medical treatment and the real activity situation in patient's everyday life. In this NIS, the course of treatment is also documented for those patients who were treated on-label with Afinitor[®], but were not included in the approval study due to previous treatment or their state of health.

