12.3 Missing values and discontinuation of treatment

Handling of missing values and dropouts is to be described and explained in the SAP.

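### Section 12.2 names Kaplan-Meier for event times in general; applied to onset times that treatment end or death can preclude, with those exits censored, it would overstate cumulative incidence

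*Protocol*

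**What the plan says.** - **Estimator.** Section 12.2: "Times of events and survival time analyses will be analysed using the Kaplan-Meier methodology". No event is named and no exception is made.
- **What is deferred.** The next sentence reads "The derivation and rating of these event times is described in the SAP". Section 12.3 adds "Handling of missing values and dropouts is to be described and explained in the SAP". The SAP is not available here.
- **Adverse events.** The sentence before the Kaplan-Meier one reads "For adverse events, incidences will be reported based on the patient population included and incidence density (number of events/sum of person times in years", by MedDRA class and term.
- **Stomatitis.** Section 5 lists "Prophylaxis and treatment of stomatitis as an adverse event during routine use of Afinitor", with its start and end dates. Section 12.1 makes stomatitis a focus of two of the three intermediate analyses, and one of these names its incidence.
- **Dose changes.** Section 5: "Number of patients where the treatment needed to be modified, interrupted or discontinued, including type of dosage modifications, duration and cause of the interruptions". The Summary (Section 3) also describes this as a number of patients.
- **Named time-to-event parameters.** These are PFS, followed to progression or death, and duration of therapy (Section 5).
- **Adverse event window.** Section 7.1 collects adverse events for 30 days after treatment ends, whatever their cause.

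**The concern.** Kaplan-Meier gives the probability of an event by time t only if those who leave the risk set could still have the event later. For first stomatitis, or first dose reduction or interruption, many patients leave because treatment has ended or they have died, and then the on-treatment event can no longer occur. If these exits are censored, the curve describes a population in which nobody stops. This study exists to describe routine care, where stopping is common.

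Stomatitis prophylaxis and management is one of three stated aims, and its dates are collected, so an onset curve is a natural output. Such a curve would sit above the crude incidence reported from the same patients. The gap would also differ between groups with different discontinuation rates, for example by physical activity or prophylaxis.

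**Working it through.** The protocol states no cumulative incidence, so there is no figure to reproduce. The check is how far 1 minus Kaplan-Meier would lie above the Aalen-Johansen cumulative incidence (CIF).

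**Inputs**
- Competing exit: exponential. The median is 7.8 months, the local PFS figure for the combination in Sections 4 and 6.3, used as a proxy for treatment end. So m = ln 2 / 7.8 = 0.0889 per month. The central figure of 11.0 months gives m = 0.0630.
- Event rates: not in the document. Assumed true 12-month CIF is 20% to 60%.
- Onset shape: Section 4 describes stomatitis as typically early. Assumed hazard a·exp(−t/τ) with τ = 0.5, 1 or 2 months, which puts about 86%, 63% or 39% of the cumulative hazard in month 1. A constant hazard is the contrasting case.

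**Formulas**, with h(t) the event hazard and H(t) its integral:
- 1 − KM = 1 − exp(−H(12))
- CIF = ∫₀¹² h(t)·exp(−H(t) − m·t) dt

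**Early onset, median 7.8 months, true CIF 45%**

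| τ (months) | a | 1 − KM | Excess (points) |
|---|---|---|---|
| 0.5 | 1.258 | 46.7% | 1.7 |
| 1 | 0.661 | 48.3% | 3.3 |
| 2 | 0.362 | 51.5% | 6.5 |

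Example, τ = 1: H(12) = 0.661 × 1 × (1 − exp(−12)) = 0.661, and 1 − exp(−0.661) = 48.3%. For a true CIF of 30% to 60% the excess runs from 1.2 points (τ = 0.5, CIF 30%) to 7.7 points (τ = 2, CIF 60%).

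**Effect of the 30-day window.** Replace m·t by m·max(t − 1, 0), so the competing exit starts to act one month later. At CIF 45% the excess falls to 0.2, 1.1 and 3.4 points. This is the favourable limit, because the window gives no further time at risk after a death. A heavier-tailed onset, Weibull cumulative hazard with shape 0.3 and net risk 30% to 70%, gives 5.0 to 8.9 points without the window and 3.8 to 6.4 with it.

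**Constant hazard λ, median 7.8 months.** Here CIF = λ/(λ + m) × (1 − exp(−12(λ + m))). For λ = 0.0518:
- CIF = 0.0518/0.1407 × (1 − exp(−1.688)) = 0.368 × 0.815 = 30.0%
- 1 − KM = 1 − exp(−0.622) = 46.3%, an excess of 16.3 points
- At 6 months: 26.7% against 21.0%, an excess of 5.7 points

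Over a true CIF of 20% to 60% the 12-month excess is 11.5 to 24.3 points. With the 11.0-month median it starts at 7.9 points (CIF 20%). The 30-day window does not help for dose changes, because no dose is left to change after treatment ends.

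**Group comparison.** Two groups with the same true CIF of 45% (τ = 1, no window), one with an 11.0-month and one with an assumed 5-month exit median, would show 1 − KM of 47.4% and 50.2%. That is an apparent difference of 2.8 points where none exists.

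**Precision.** The binomial SE at 45% is √(0.45 × 0.55/3000) = 0.9 points for the full cohort and √(0.45 × 0.55/500) = 2.2 points for an intermediate analysis of about 500 patients.

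**The case against.** The strongest reply is that the protocol plans no such curve. Stomatitis is handled as an adverse event, by crude incidence and incidence density, and dose changes are counted. Time to first stomatitis and time to first dose change are named nowhere. The two time-to-event parameters that are named suit Kaplan-Meier. This stands, so a reader should not infer that 12.2 fixes 1 minus Kaplan-Meier as the study's stomatitis or dose-change incidence.

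Second, the bias depends on how exits are rated, and that is left to the SAP. Rating could make treatment end part of a composite event. It could also keep patients with a competing event at risk until the administrative cut-off of 31/12/2017, in which case Kaplan-Meier returns the cumulative incidence. This also stands: naming the estimator does not by itself create the bias. But the protocol hands over derivation and rating, not the choice of estimator, and its general wording invites ordinary censoring at treatment end.

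Third, a reader might add stomatitis resolution to the list of precluded events. That is wrong: stomatitis can resolve after treatment stops, and Section 7.1 records duration and outcome. Nor does treatment end at once preclude a recorded stomatitis, given the 30-day window.

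Fourth, Section 12.1 makes all results descriptive, and a net on-treatment risk is a legitimate quantity if labelled as such. That limits the weight of the point but does not remove it, because a descriptive figure should still describe what happened.

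**Conclusion.** The point holds in conditional form and is minor. The Kaplan-Meier sentence in 12.2 is wider than it should be. If it is followed for onset times that treatment end or death can preclude, with those exits censored, the error is always upward.

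The size rests on assumptions: event rates and onset shapes that the document does not give, and PFS medians standing in for time on treatment. With a 7.8-month median, about 1 to 6 points is a fair summary for early-onset stomatitis. Very short onset together with the full 30-day window brings it close to zero, and slower onset with high incidence and no window takes it somewhat above 6. For constant-hazard events it is about 10 points or more.

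A reader might infer that the shift must be many standard errors. The documents do not support that. The smallest excesses are below one SE in an analysis of about 500 patients (1.7 against 2.2 points), and the larger multiples depend on late or constant onset, which does not fit the protocol's own description of stomatitis.

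**What to change.** In Section 12.2, limit Kaplan-Meier to PFS and all-cause times such as duration of therapy. Add that any analysis of time to first stomatitis, or to first dose reduction or interruption, will use the Aalen-Johansen cumulative incidence. The competing events are death and treatment end; for adverse events, the end of the 30-day window replaces treatment end. Stomatitis resolution should not be listed as precluded by treatment end. The crude incidence, incidence density and patient counts stay as they are.

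The cost is one sentence and a standard option in SAS; no new data are needed. The small downside is that the figures will not be directly comparable with reports that used Kaplan-Meier.
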